4. STATISTICAL BASIS FOR SAMPLE SIZE

The sample size for this study is driven by the lot-to-lot consistency requirement. A total of 800 subjects in each of the three Sci-B-Vac™ lots will provide at least 90% power to ensure that the 95% confidence interval for each pairwise difference (GMC of anti-HBs in group A/GMC of anti-HBs in group B, GMC of anti-HBs in group A/ GMC of anti-HBs in group C, GMC of anti-HBs in group B/ GMC of anti-HBs

PAREXEL International Statistical Analysis Plan

in group C) in normalized log₁₀ (GMC) will have a lower bound that is >-0.176 and an upper bound that is <0.176 if the true standard deviation is ≤ 0.9 ; this corresponds to the true GMC ratio falling between $2/3$ and $3/2$. With an active comparator arm of Engerix-B[®] of equal size ($n=800$), the total sample size of the study is 3,200.

If lot-to-lot consistency is demonstrated, all three Sci-B-Vac[™] lots will be pooled together to test that the Seroprotection Rate (SPR) four weeks after completion of the three-dose regimen of Sci-B-Vac[™] is non-inferior to a three-dose regimen of Engerix-B[®]. Assuming 10% of the subjects are non-evaluable (i.e., 2880 are evaluable, with 2160 randomized to Sci-B-Vac[™] and 720 to Engerix-B[®]), a two-sided 5% significance level and a non-inferiority margin of -5% , the non-inferiority test will have $> 90\%$ power. The following table provides the estimated power under different assumptions of the SPR four weeks after completion of the three-dose regimens.

Response in Engerix-B [®] (N=720)	Response in Sci-B-Vac [™] (N=2160)	Power
80%	85%	99%
85%	85%	92%
90%	95%	99%

In October 2018, enrollment was closed early for non-safety-related reasons after 2838 were randomized to the study. With approximately 700 subjects in each of the three Sci-B-Vac[™] lots and 700 subjects in comparator arm of Engerix-B[®], the sample size will provide $> 80\%$ power to evaluate both the primary objective of lot to lot consistency of the three Sci-B-Vac lots, and the secondary objective of non-inferiority of Sci-B-Vac[™] vs Engerix-B[®].

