6.2.5 Per Protocol Sets

6.2.5.1 Per Protocol Set 1 (PPS1)

All subjects in the FAS who:

- received all 3 vaccinations
- have an evaluable serum immunogenicity samples at baseline and at the time point of interest
- are seronegative at baseline
- had no major protocol deviations leading to exclusion, which will be identified prior to unblinding.

A major protocol deviation for the purpose of exclusion from the PPS1 is defined as a protocol deviation that is considered to have a significant impact on the immunogenicity result of the subject.

These will be identified prior to unblinding and analysis and may include:

- subjects enrolled who did not meet study entry criteria
- subjects who did not receive the correct treatment
- subjects who developed withdrawal criteria but were not withdrawn
- subjects who received a prohibited concomitant medication

PAREXEL International Statistical Analysis Plan

- subjects with a deviation identified through monitoring visits or otherwise, where the deviation is judged to impact the reliability of subject immunogenicity results

PPS1 will be used for the primary endpoint analysis.

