6.2.5.2 Per Protocol Set 2 (PPS2)

All subjects in PPS1, but excluding those who attended study visits outside of the following windows:

- V3/Day 168 (+/- 28 days)
- V4/Day 196 (-7/+14 days)

PPS2 will be used for the primary, secondary, and exploratory endpoints.

In case of vaccination error, subjects in PPS1 and/or PPS2 will be analyzed “as randomized” and the subject who received the wrong vaccination will be excluded from PPS1 and/or PPS2. If a subject receives a vaccine from the wrong kit number, but the same as the one the subject was randomized to, the subject will not be removed from PPS1 and/or PPS2.

If a subject is unblinded during the study, except for suspected unexpected serious adverse reaction (SUSAR), he/she may be excluded from PPS1 and/or PPS2 based on sponsor’s decision with respect to any potential bias that may be introduced in the analysis of the primary and key secondary immunogenicity analyses.

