6.3.2 Statistical Significance Level

All statistical tests will be two-sided and will be performed at the 5% level of significance, unless otherwise stated.

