6.3.13 Immunogenicity

The primary analysis of the immunogenicity data will be based on PPS1 and PPS2. Sensitivity analyses using the same modeling approach will be conducted using the FAS. These analyses will be reported both with and without patients in the FAS who are seropositive at baseline.

Immunogenicity (measurement of anti-HBs titer) data will be listed by subject including actual sampling times relative to dosing. Serum concentrations will be summarized by Sci-B-Vac™ lot, Sci-

PAREXEL International

Statistical Analysis Plan

B-Vac™ treatment group and Engerix-B® treatment group. The following descriptive statistics will be presented for serum concentrations obtained at each time point: n, geometric mean, geometric SD, median, minimum and maximum values.

Individual serum concentration versus actual times will be plotted by Sci-B-Vac™ lot, Sci-B-Vac™ treatment group and Engerix-B® treatment group for anti-HBs antibody in linear and semi-logarithmic scale. The geometric mean serum concentrations with corresponding 95% confidence intervals versus times will also be presented. The bar plot of SPR by treatment on Days 168, 196 and 336 will also be produced based on PPS2. All treatment groups will be overlaid on the same plot.

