6.3.13.1 Primary Hypothesis

The lot-to-lot equivalence, in terms of immunogenicity, of three independent consecutive lots of the Sci-B-Vac™ will be demonstrated if the following condition is satisfied:

The upper and lower bound of the two sided 95% CI of the geometric mean concentration (GMC) of anti-HBsAg antibody ratios 4 weeks after the third injection for all three pairwise comparisons (GMC(group A)/GMC(group B), GMC(group A)/GMC(group C), GMC(group B)/GMC(group C)) are within [0.67, 1.5]

The analysis will use a two-sided 5% significance level. PPS1 and PPS2 will be used to test the primary hypothesis.

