6.3.13.2 Statistical Methods for Primary Immunogenicity Analyses

Geometric mean concentration (GMC) of anti-HBsAg antibody ratios 4 weeks after the third injection

All statistical analyses will be performed on the logarithmically (base 10) transformed values.

Adjusted estimates of GMCs and their associated 95% CIs will each be determined using an analysis of covariance (ANCOVA) model with a factor for vaccine lot group, and a covariate for the log transformed pre-vaccination (baseline) titer. Data from all centers will be pooled. For each vaccine lot, antibody GMCs, associated standard errors, two-sided 95% CIs and median, minimum, and maximum titer values will be determined and presented by lot group. The median, minimum, and maximum values will be reported on the actual titer values, rather than the log scale. The ratio in GMCs between each vaccine lot group (GMC(group A)/GMC(group B), GMC(group A)/GMC(group C), GMC(group B)/GMC(group C)), and their associated two-sided 95% CIs will also be presented.

PAREXEL International

Statistical Analysis Plan

Sensitivity analyses using the same modeling approach outlined above will be conducted using the FAS. These analyses will be reported both with and without patients in the FAS who are seropositive at baseline.

If this condition is satisfied with either PPS1 or PPS2, then manufacturing equivalence (lot-to-lot consistency) will be demonstrated.

Sample SAS code for assessment of lot-to-lot equivalence:

- Sample SAS code for ANCOVA model:

```
PROC MIXED;  
CLASS treatment;  
MODEL log (var) = treatment log (baseline of var);  
LSMEANS treatment / DIFF CL ALPHA=0.05;  
ODS OUTPUT LSMEANS=ls_means Diffs=diff;  
QUIT;
```

where var represent the anti-HBs titer and treatment represents vaccine lot group.

6.3.13.3 *Secondary Objective Analyses*

If lot-to-lot consistency is demonstrated, then the data from the three lots will be combined to address the secondary immunogenicity non inferiority-hypothesis. It is to demonstrate that the SPR 4 weeks after completion of the three-dose regimen of Sci-B-Vac™ is non-inferior to the SPR 4 weeks after completion of a three-dose regimen of Engerix-B®. Seroprotection is defined as anti-HBs levels ≥ 10 mIU/mL in serum. Seroprotection rate (SPR) is the percentage (%) of subjects achieving seroprotection.

Seroprotection rate (SPR) 4 weeks after the third injection

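### Lot consistency may be claimed on either PPS1 or its subset PPS2, each at the full level, with no lead set named

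*SAP*

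**What the plan says.** The primary criterion is that the two-sided 95% confidence intervals of the GMC ratios lie within 0.67 to 1.5 "4 weeks after the third injection for all three pairwise comparisons" (SAP 6.3.13.1). Five places say which analysis set applies:

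- 6.2.5.1: "PPS1 will be used for the primary endpoint analysis".
- 6.2.5.2: "PPS2 will be used for the primary, secondary, and exploratory endpoints". The same section defines PPS2 as PPS1 without subjects whose Visit 3 or Visit 4 fell outside stated windows, so PPS2 is nested in PPS1.
- 6.3.13: "The primary analysis of the immunogenicity data will be based on PPS1 and PPS2".
- 6.3.13.1: "PPS1 and PPS2 will be used to test the primary hypothesis".
- 6.3.13.2: "If this condition is satisfied with either PPS1 or PPS2, then manufacturing equivalence (lot-to-lot consistency) will be demonstrated".

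Only the last gives a pass rule. On the level, 6.3.2 states: "All statistical tests will be two-sided and will be performed at the 5% level of significance, unless otherwise stated". Section 6.3.13.1 repeats the two-sided 5% level for the primary hypothesis. Nothing visible splits the level or puts the sets in order.

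Under 6.3.13.3, a successful lot comparison opens the pooled seroprotection (SPR) non-inferiority test, which is run in PPS2.

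**The concern.** A rule under which either of two sets suffices, each at full level, cannot have a lower false-equivalence rate than one named set. It has a higher rate whenever the two sets can disagree. Fixing the rule in advance does not remove the second chance.

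Three things are at stake:

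- **Error rate.** Each bound of a 95% interval carries a one-sided 2.5% error. The question is whether the combined rule stays within that.
- **The primary result.** If one set passes and the other fails, the objective is met on the favourable set, and the SAP does not say whose intervals are the primary estimate.
- **Alignment.** The four sections that name both sets could be read as requiring both; 6.3.13.2 says one is enough. In addition, a pass in PPS1 only would open the SPR test in PPS2, where the lot criterion was not met. This last point is minor and does not raise the SPR test's own error rate.

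**Working it through.** **Inputs from the SAP.** Limits 0.67 to 1.5 (log10: -0.1739 to 0.1761), all three pairs, 95% intervals (6.3.13.1). Log10 SD of 0.9 or less, planning limits of ±0.176, 800 per lot planned and about 700 per lot after early closure (section 4). Section 4 also assumes 10% non-evaluable, for the non-inferiority calculation; applied here, 700 × 0.9 = 630 per lot.

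**Assumptions.** The share f of PPS1 retained in PPS2 is not stated: 90% is used, with a range of 98% to 80%. SDs below 0.9 are assumed values within the stated range. Out-of-window subjects are taken to respond like the rest. Normal approximation throughout.

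**Step 1: the plan's own power.** For one pair with equal lots, SE = SD × √(2/n) and power = 2Φ(0.176/SE − 1.96) − 1.

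- n = 800: SE = 0.0450, 0.176/SE = 3.911, power 0.949. This agrees with the stated 90% or more for each pair.
- n = 700: SE = 0.0481, 0.176/SE = 3.659, power 0.911.
- All three pairs jointly, by simulation: 0.876 at 800 and 0.795 at 700.

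**Step 2: ceiling for one pair at its margin.** With nested sets the two test statistics have correlation √f, and P(either passes) = 2 × 0.025 − P(both pass). This gives 2.8% at f = 98%, 3.0% at 95%, 3.2% at 90% and 3.5% at 80%, against 2.5% for one set.

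**Step 3: the three-pair rule as planned.** PPS2 was simulated as a random subset of PPS1. The extreme lots have a true ratio of 1.5, the third lot is midway (the worst case), and f = 90%.

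| SD | n = 700: PPS1 alone | n = 700: either | n = 630: PPS1 alone | n = 630: either |
|---|---|---|---|---|
| 0.9 | 1.91% | 2.46% | 1.79% | 2.31% |
| 0.8 | 2.12% | 2.74% | 2.03% | 2.62% |
| 0.7 | 2.31% | 2.98% | 2.25% | 2.90% |
| 0.6 | 2.43% | 3.14% | 2.40% | 3.10% |

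At SD 0.9 and 700 per lot, the either rule crosses 2.5% when f falls to about 88% (2.50% at 88%, 2.55% at 85%, 2.62% at 80%). At SD 0.9 and 630 per lot it stays below 2.5% for every f from 98% to 80%. With the third lot at one end instead of midway, the rates are about 0.5% for PPS1 alone and 0.5% to 0.7% for either.

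**Step 4: joint power under each rule.** Equal lots, SD 0.9, f = 90%, limits 0.67 to 1.5.

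| Rule | n = 700 | n = 630 |
|---|---|---|
| Either, 95% intervals | 0.81 | 0.73 |
| PPS1 alone | 0.79 | 0.70 |
| PPS2 alone | 0.71 | 0.61 |
| Both required | 0.68 | 0.58 |
| Either, 96.25% intervals | 0.76 | 0.68 |

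**Step 5: level needed to keep the either rule.** Setting the Step 2 expression to 0.025 and solving for the per-set level gives intervals of 95.6% at f = 98%, 96.2% at 90% and 96.5% at 80%. Because the three-pair event lies inside the one-pair event, these levels cap the error at any SD.

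**The case against.** The strongest reply is that little is lost. At the planning SD of 0.9 with 700 per lot and 90% overlap, the either rule stays just under 2.5%. At 630 per lot it stays under at every overlap tried. Going above 2.5% needs a smaller SD or a lower overlap, plus a third lot placed near the middle, and even then the excess in the table is at most about 0.6 points. All of this stands, and it limits the severity. It does not rescue the rule: section 4 allows SDs below 0.9, and the rate is above that of one named set at every SD.

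A second reply is that the sections do not truly conflict, because four are general and 6.3.13.2 gives the specific rule. That is a fair reading, and on it the outcome of a disagreement is defined: one pass suffices. The general sections still use *and* where the rule uses *either*, and joint power at 700 per lot is 0.68 under one reading and 0.81 under the other. They should say the same thing.

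Third, the adjusted levels in Step 5 come from a one-pair ceiling and over-correct at SD 0.9. That is correct, and is a reason to prefer naming one set. The power costs are also shown where power is lowest: at SD 0.8 and 700 per lot, joint power is about 0.92 for PPS1 alone and 0.93 for either.

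Finally, the power statement in section 4 may be meant per pair, in which case 0.91 at 700 per lot satisfies it. That stands: the figure is unclear, not shown to be wrong.

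**Conclusion.** The concern holds. The SAP gives the primary claim two chances at full level and names no deciding set. The increase in false equivalence is modest: about 0.5 to 0.7 percentage points over PPS1 alone at 90% overlap in the worst-case lot arrangement. It takes the rate above 2.5% at SDs of 0.8 and below, but not at 0.9 unless the overlap is about 88% or less with 700 per lot.

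These sizes rest on the assumed overlap, the assumed SDs and the assumption that out-of-window subjects respond like the others. If those subjects differ between lots, the choice of set could matter more. That the favourable set decides, and that the primary intervals are not identified, depends on none of these assumptions. This should be fixed before unblinding.

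**What to change.** Replace the either-set sentence in 6.3.13.2 with one deciding set. Suggested wording: *The lot-to-lot claim rests on PPS1 alone; results in PPS2 and the FAS are supportive and cannot replace it.* Bring 6.2.5.1, 6.2.5.2, 6.3.13 and 6.3.13.1 into line.

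In 6.3.13.3, state how the PPS1 result opens the SPR test. Either run that test in PPS1 (6.2.5.2 then changes too), or keep it in PPS2 and require the lot criterion there as well. Under the second option the test opens with probability 0.68 at 700 per lot and 0.58 at 630 (equal lots, SD 0.9, 90% overlap).

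Alternatives:

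- Name PPS2 as the single set. This also matches the set used for the SPR test, but joint power falls to 0.71 / 0.61.
- Keep the either rule with a stated, adjusted interval level in each set, fixed from the overlap counted before unblinding (about 96.2% if it is 90%). Joint power is then about 0.76 / 0.68.

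Naming PPS1 is the cheapest: joint power goes from 0.81 to 0.79 at 700 per lot and from 0.73 to 0.70 at 630. Whichever is chosen, section 4 should say whether its figure of more than 80% "power to evaluate both the primary objective of lot to lot consistency of the three Sci-B-Vac lots" is per pair or joint, and give the joint power for the chosen rule. Read as joint at 700 per lot, it is met under the either rule but narrowly missed by PPS1 alone (0.79; 0.795 with the ±0.176 limits of section 4). The cost is SAP wording only.

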6.3.13.4 Exploratory Objective Analyses

Analysis of all exploratory immunogenicity endpoints will be based on PPS2, unless otherwise indicated. Exploratory efficacy endpoints will be summarized and analyzed without adjustment for multiple comparisons.

Each of the exploratory endpoints defined in the protocol will be summarized for each Sci-B-Vac™ lot separately, as well as for the difference between each Sci-B-Vac™ lot. Analysis of GMC endpoints will use the same methods as described above for the primary endpoint. For binary data, proportions and two-sided 95% CIs will be reported. The difference in proportions and two-sided 95% CIs, will be calculated using the Miettinen and Nurminen method.

In addition, each of the exploratory endpoints will be summarized with data from all 3 lots of Sci-B-Vac™ pooled together. Summaries will be presented for Sci-B-Vac™, Engerix-B™ and for the treatment difference. Adjusted estimates of GMCs and their associated 95% CIs will each be determined using an analysis of covariance (ANCOVA) model with a factor for treatment group, and a covariate for the log transformed pre-vaccination (baseline) titer. For each treatment group, anti-HBs GMCs, associated standard errors, two-sided 95% CIs and median, minimum, and maximum titer values will be determined and presented by treatment group. The median, minimum, and maximum values will be reported on the actual titer values, rather than the log scale. The ratio in GMCs between treatment groups (GMC of anti-HBs in Sci-B-Vac™ / GMC of anti-HBs in Engerix-B®), and their associated two-sided 95% CIs will also be presented. For binary data, proportions and two-sided 95% CIs will be reported. The difference in proportions and two-sided 95% CIs, will be calculated using the Miettinen and Nurminen method.

Please see [Section 6.3.13.2](#) and [Section 6.3.13.3](#) for sample codes. Per sponsor's request, one additional pre-specified exploratory analysis has been added to the SAP. This additional exploratory analysis is as follows:

PAREXEL International
Statistical Analysis Plan

- To determine whether the SPR after 2 vaccinations with Sci-B-Vac™, evaluated 20 weeks after the second vaccination (just prior to receiving the third vaccination), is non-inferior to the SPR 4 weeks after receiving the third vaccination with Engerix-B®.

This additional exploratory analysis will be summarized with data from all 3-lots of Sci-B-Vac™ pooled together.

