2. STUDY DESIGN

This is a double-blind 4-arm randomized study. Subjects age 18-45 years will be randomly assigned to one of 3 lots of Sci-B-Vac™ or to Engerix-B® with a ratio 1:1:1:1 using a web-based randomization system to be immunized against Hepatitis B virus (HBV), according to a three-dose immunization schedule and followed for 24 weeks after the third immunization. The total study duration for each subject (assuming a screening period of 28 days or 4 weeks) is 364 days or 52 weeks.

The scheme of the study design is as Figure 1. For further details please refer to [section 3.1 of the Protocol](#).

PAREXEL International Statistical Analysis Plan

Figure 1: Schematic of Study Design

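### The Sci-B-Vac/Engerix-B GMC ratio uses one residual variance in a 3:1 comparison, so its 95% CI is right only if both vaccines have the same log-titer SD

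*SAP*

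**What the plan says.** SAP Section 2 randomizes subjects to three Sci-B-Vac lots and Engerix-B "with a ratio 1:1:1:1 using a web-based randomization system". Under Section 6.3.13.4 each exploratory endpoint is also "summarized with data from all 3 lots of Sci-B-Vac™ pooled together" and set against Engerix-B. The GMCs and their CIs are "determined using an analysis of covariance (ANCOVA) model with a factor for treatment group, and a covariate for the log transformed pre-vaccination (baseline) titer", and the Sci-B-Vac/Engerix-B ratio is reported with a two-sided 95% CI.

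For code, Section 6.3.13.4 refers back to Sections 6.3.13.2 and 6.3.13.3. The GMC code in 6.3.13.2 has a CLASS statement, "MODEL log (var) = treatment log (baseline of var") and "LSMEANS treatment / DIFF CL ALPHA=0.05". It has no REPEATED / GROUP= statement, no EMPIRICAL option and no DDFM setting, so one residual variance is estimated for both groups. The FAS sensitivity analyses in Sections 6.3.13 and 6.3.13.2 keep the same model. Nothing in the SAP allows for unequal variances.

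Section 4 gives the sizes. The plan assumed "2880 are evaluable, with 2160 randomized to Sci-B-Vac[™] and 720 to Engerix-B". After enrollment closed early, about 700 subjects per arm are stated, which is about 2100 against 700. The only log10 SD in the SAP (at most 0.9) is given for the Sci-B-Vac lots.

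**The concern.** The code was written for the lot comparison, where the arms are equal in size. Section 6.3.13.4 carries it over to a comparison that pooling has made 3:1. There the single variance estimate takes three quarters of its weight from Sci-B-Vac, while the smaller Engerix-B arm contributes most of the uncertainty of the ratio (three quarters of it when the SDs are equal). If the two SDs differ, the model's standard error is wrong, and more subjects would not correct it.

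At stake is the coverage of the CIs for the vaccine-to-vaccine GMC ratios, including those in the sub-groups of interest. These are descriptive results, but they compare two vaccines and readers will take the intervals at face value.

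**Working it through.** **Inputs.** From the SAP: allocation 1:1:1:1 (Section 2); three lots pooled (6.3.13.4); 2160 vs 720 planned and about 2100 vs 700 actual (Section 4); log10 SD at most 0.9 for the lots and margin ±0.176 (Section 4); two-sided 95% CI (6.3.13.4). Assumed: r = SD Engerix-B / SD Sci-B-Vac, which the SAP does not give; range 0.8 to 1.2. The baseline covariate is left out of the algebra. The exploratory analyses use PPS2, whose subjects are seronegative at baseline, so it has little room to explain variance.

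**The plan's own figure.** No figure is stated for the vaccine ratio. The one figure that uses the log10 SD is the lot power of at least 90% per pair with 800 per lot:
- SE = 0.9 × √(2/800) = 0.045
- Power = 2Φ(0.176/0.045 − 1.96) − 1 = 2Φ(1.951) − 1 = 94.9%

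This agrees with the SAP for each pair.

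**Model SE against true SE.** Let s be the Sci-B-Vac SD, 3n the size of the pooled Sci-B-Vac group and n that of Engerix-B.
- Common variance: sp² ≈ s²(3 + r²)/4
- Model SE² = sp²(1/(3n) + 1/n) = s²(3 + r²)/(3n)
- True SE² = s²/(3n) + r²s²/n = s²(1 + 3r²)/(3n)
- Model SE / true SE = √[(3 + r²)/(1 + 3r²)]
- Coverage = 2Φ(1.96 × SE ratio) − 1

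The group size n cancels, so coverage depends only on r and the 3:1 split. With two equal groups the same algebra gives an SE ratio of 1 for any r.

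| r | SE ratio | Coverage | CI factor from model | CI factor needed |
|---|---|---|---|---|
| 0.8 | √(3.64/2.92) = 1.117 | 97.1% | 1.184 | 1.164 |
| 0.9 | √(3.81/3.43) = 1.054 | 96.1% | 1.189 | 1.178 |
| 1.0 | 1 | 95.0% | 1.194 | 1.194 |
| 1.1 | √(4.21/4.63) = 0.954 | 93.8% | 1.199 | 1.210 |
| 1.2 | √(4.44/5.32) = 0.914 | 92.7% | 1.205 | 1.227 |

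The CI factor is what the estimated ratio is multiplied and divided by: 10^(1.96 × SE) at 2100 vs 700 with s = 0.9.

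**Simulation (20,000 runs, 2100 vs 700).** At r=1.2 the common-variance CI covers 92.8% and a separate-variance CI 95.1%. At r=1.0 both cover 94.8%. A separate-variance CI estimates the true SE² above directly, so it is right for r below 1 as well.

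**Each arm's own GMC.** The same model supplies these CIs. For Engerix-B the SE ratio is √[(3 + r²)/4]/r. This gives 0.933 and 93.2% coverage at r=1.1, and 0.878 and 91.5% at r=1.2.

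**The case against.** The strongest reply is that the SAP offers no evidence that the SDs differ. It gives none for Engerix-B, a common-variance ANCOVA on log titers is conventional, and the code is labelled a sample. No decision rests on the ratio: it is exploratory, with no margin or multiplicity adjustment. Section 6.3.13 also reports the geometric SD by treatment group, so a reader could see an imbalance. At r=1.2 the interval factor is 1.205 where 1.227 is needed, which would rarely change how the ratio is read. All of this stands, and it limits the point to low severity.

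A reader might go further and infer that Engerix-B must be the more variable arm, so that the CI is too narrow. Two of the three power rows in Section 4 give Engerix-B the lower response (80% vs 85%, 90% vs 95%), and Section 6.1.1 sets values below LQ to LQ/2, so extra non-responders form a low cluster. The documents do not settle this. Take a fraction p of non-responders at LQ/2, and responders with SD s whose mean lies d above LQ/2 on the log10 scale. The variance is then (1 − p)s² + p(1 − p)d². With assumed LQ 5, Sci-B-Vac responder mean 2.5 to 3.0 and s = 0.6 to 0.8:
- 10% vs 5% non-responders, equal responder means: r = 1.09 to 1.19, coverage 92.8 to 93.9%.
- The same, Engerix-B responder mean 0.5 log10 lower: r = 0.99 to 1.04, coverage 94.5 to 95.1%.
- 20% vs 15%, Engerix-B responder mean 0.5 log10 lower: r = 0.90 to 0.93, coverage 95.8 to 96.2%.

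The SAP's third row (85% in both arms) gives r=1 by this mechanism if responder means are equal. The direction therefore depends on responder titers that the SAP does not state. Nor does it support an SD ratio well above 1.2, or a larger problem after two doses: with many values at LQ/2, the floor could as well compress the weaker arm.

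**Conclusion.** The point holds in a two-sided, low-severity form. As written, the Sci-B-Vac/Engerix-B GMC ratio has a true 95% CI only if the two log-titer SDs match. Under assumed SD ratios of 0.8 to 1.2, coverage runs from 97.1% down to 92.7%. The size rests on r, which is an assumption, and on the 3:1 split, which is in the SAP.

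It should not be read as showing that the interval is too narrow, or that a trial conclusion is at risk. The 3:1 imbalance does not arise in the primary comparison of equal-sized lots. The SPR non-inferiority test uses the Miettinen-Nurminen interval and does not use this model. The reason to act is that a better method costs almost nothing and is best fixed before unblinding.

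**What to change.** For the treatment-group GMC models in Section 6.3.13.4 only, fit a separate residual variance per vaccine. In the PROC MIXED code add a REPEATED / GROUP=treatment statement and put DDFM=SATTERTHWAITE on the MODEL statement. Say so in one sentence of 6.3.13.4, because the present reference to the 6.3.13.2 code would otherwise carry the common variance over. Leave the lot-comparison code as it is.

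The cost is one line of code, one option and one sentence. Coverage returns to about 95% whichever vaccine is more variable. If the SDs are equal, the CI is practically unchanged.
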